4.0 Study Endpoints/Events/Outcomes

- 4.1 Primary Endpoint/Event/Outcome: To determine if LB plus bupivacaine in an interscalene block results in less opioid use over 72 hours compared to bupivacaine only for RCR surgery.
- 4.2 Secondary Endpoint(s)/Event(s)/Outcome(s):
 - To determine if LB plus bupivacaine in an interscalene block results in less pain over 72 hours as compared to bupivacaine only in an interscalene block for RCR surgery. Assessed via total pain scores
 - To determine if LB plus bupivacaine in an interscalene block results in improved QOR at 72 hours as compared to bupivacaine only in an interscalene block for RCR surgery. Assessed via QOR 15 patient survey.
 - To determine if LB plus bupivacaine in an interscalene block results in fewer phone calls to the surgeon within 72 hours as compared to bupivacaine only in an interscalene block for RCR surgery.
 - To determine if LB plus bupivacaine in an interscalene block hastens readiness for hospital discharge compared to bupivacaine only in an interscalene block for RCR surgery. Study Intervention(s)/Investigational Agent(s)
- 4.3 Description: LB is a long acting local anesthetic. It is liposome encapsulated bupivacaine which allows for prolonged release of bupivacaine over a 72

PROTOCOL TITLE: Prospective Randomized controlled study comparing liposomal bupivacaine to bupivacaine interscalene blocks for arthroscopic rotator cuff repair surgery

VERSION DATE: 8/5/2020

hour period. Bupivacaine is a medium acting local anesthetic which provides between 6 and 24 hours of analgesia when used in a peripheral nerve block. Both medications are standard of care for use in interscalene blocks here at the U of MN. Acetaminophen is a medication used to treat pain, gabapentin is a gabapentinoid which is used to treat postoperative pain.

4.4 Drug/Device Handling: The LB will be stored in a locked pyxis fridge in a box labeled study LB. It will be retrieved by the PI and sub I's for use in the interscalene blocks.

- The LB will be stored in a locked pyxis fridge in a box labeled Liposomal Bupivacaine. The anesthesiologists in charge of regional anesthesia the day the procedure will be informed will write the order for dispensing the medication and the block per standard of care. It will be retrieved by the PI and sub I's for use in the interscalene blocks.

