4.5 Biosafety: n/a

4.6 Stem Cells: n/a

5.0 Procedures Involved

5.1 Study Design: **Level I randomized prospective outcomes study comparing two groups of patients. One group will receive LB plus bupivacaine for an interscalene block. The other will receive bupivacaine for an interscalene block injection.**

Study Procedures: Patients will be identified in the pre-operative time period by the surgeons and if possible will be consented by the research coordinator or research assistant. If that is unable to be accomplished the patient will be introduced to the study and given a copy of the consent form to evaluate prior to surgery. On the day of surgery, the research coordinator, research assistant or primary or sub investigators will determine if the patient has any questions so that they can be answered. After discussion with the person obtaining consent, consent will be obtained in the pre-operative area. A random number generator will be used to determine if the patient will have LB plus bupivacaine or bupivacaine for their interscalene block. The primary investigator will access the number generator in the pre-op area immediately prior to block placement. The website www.random.org will be used as the random number generator.

Treatment technique:

All patients will receive preoperative oral multimodal medications consisting of acetaminophen 975 mg and gabapentin 300 mg.

After completion of the preoperative process the patient will be placed in the supine position with the head of the bed elevated 30 degrees with standard ASA monitors applied. Sedation will be provided with midazolam 0-2 mg and propofol 50 mg. The

PROTOCOL TITLE: Prospective Randomized controlled study comparing liposomal bupivacaine to bupivacaine interscalene blocks for arthroscopic rotator cuff repair surgery

VERSION DATE: 8/5/2020

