interscalene groove will be identified with the ultrasound. Using sterile technique, a 21g Nerve block needle will then be inserted and advanced under ultrasound guidance until it is in the interscalene groove. Once in the interscalene, 20 mL of local anesthetic will be injected, with 10 mL deposited at the top of the brachial plexus and 10 mL at the bottom. In the study group, 5 mL of each 0.5% bupivacaine and LB will be injected at each location. The control group will have 20 mL of 0.5% bupivacaine divided between the injection sites (10 mL at each site). The patient will be monitored in the preoperative area until he/she is brought into the operating room for their procedure. A working block prior to surgery will be confirmed via sensory testing of the shoulder.

All patients will undergo a standard induction with propofol 1.5-3.0 mg/kg, ondansetron 4 mg, dexamethasone 10 mg and ketamine 0.25 mg/kg. A MAC or general LMA or ETT will be placed and an opioid sparing technique will occur. Standardized maintenance will be a propofol infusion without neuromuscular blockers. 25-50 mcg of IV Fentanyl will be utilized for increases in heart rate greater than 20% or increases in systolic blood pressure above baseline.

Once in the operating room the surgeon will use an additional 10 mL of 0.25% bupivacaine for skin, subcutaneous, and intraarticular injection.

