When the operation is complete, the patient will be woken up and brought to the PACU. There the patient will receive IV fentanyl for a pain score of greater than 7 (50 mcg of Fentanyl x 2 if needed). If more than 100 mcg of fentanyl is given and pain still remains above a 7 then IV hydromorphone will be used (max dose of 1 mg and given in increments of 0.3 mg q 10 minutes prn severe pain). Once the patient is able to tolerate oral medications a dose of 5 mg of oral oxycodone (or 2 mg of oral hydromorphone if allergic to oxycodone) will be given if their pain score is greater than 4 (on the Visual Analog Scale). Once the patient meets discharge criteria, they will be discharged home where each day they will fill out a pain diary. Additionally, a member of the research team will call the patient for signs of complications and ask the patient their current pain score, total opioid pills taken and non-opioid pain medication taken at 24, 48, and 72 hours postoperatively. Additionally, they will perform a Quality of Recovery Score survey at 72 hours, and 14 days postoperatively. An Ultrasound of the diaphragm will be completed by a blinded anesthesiologist in the PACU to assess diaphragm function. All patients will be discharged with instructions to take acetaminophen 975 mg q8 hours & ibuprofen 600 mg q6 hours. Additionally they will have opioid pain medication to take as needed for pain greater than 4. They will either have hydromorphone 2mg, 30-40 pills, with dosing being 1-2 pills q4 hours prn severe pain. Or they will have a prescription for oxycodone 5 mg, 30-40 pills, dosing 1-2 pills q 4 hours prn severe pain.

Enrollment procedures: Patients will be identified in the pre-operative time period by the surgeons and if possible will be consented by the research coordinator or research assistant. If that is unable to be accomplished the patient will be introduced to the study

PROTOCOL TITLE: Prospective Randomized controlled study comparing liposomal bupivacaine to bupivacaine interscalene blocks for arthroscopic rotator cuff repair surgery

VERSION DATE: 8/5/2020

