and given a copy of the consent form to evaluate prior to surgery. On the day of surgery, the research coordinator, research assistant or primary or sub investigators will determine if the patient has any questions so that they can be answered. After discussion with the person obtaining consent, consent will be obtained in the pre-operative area. Subjects interested in the study will be presented with consent and Health and Insurance Portability and Accountability Act (HIPAA) forms. The patient will review the forms with the surgeon, research staff, or anesthesiologist. Subjects will be reminded that participation is completely voluntary, and that they may stop participation at any time without question or penalty. The surgeon, research staff, or anesthesiologist will answer any questions that the subjects may have about the study. If the patient decides to participate, they will be asked to sign the consent and HIPAA forms. One copy will be saved for study records, and the subject will be provided with a copy of the forms for their own records. The patient will then have an opportunity to ask any questions of the surgeon regarding the treatment option that has been selected. All forms will be locked and stored in a file cabinet in the research department. Enrollment will proceed from July 2018 to July 2019. Enrolling consecutive patients will help reduce selection bias.

Assessments: Post-operatively patients will be evaluated at 2 and 6 hours post-operatively by a blinded research staff. This person will not be aware of the patient's mode of analgesia. The patients will be contacted via in person assessment or via telephone at 24, 48, and 72 hours +/- 5 hours. Patients will be asked to rate their pain on scale of 0-10. The amount of opioids used by the patient will be recorded as will any other adjuvant pain medication used. The time in phase 1 and phase 2 of PACU will be recorded. The patients will be asked at 72 hours post-injection if they would undergo interscalene block with their medication again or if they would opt for a different form of pain management. Patients will fill out a Quality of Recovery Survey at 72 hours and 14 days, and be assessed for block related complications at this time. All complications will be recorded including:

- Failure of the block
- Wound infections
- Subsequent procedures

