- Complications related to placement of the interscalene block including nerve injury, prolonged sensory loss greater than 3 days, prolonged arm weakness greater than 3 days
- Opioid related side effects of nausea and/or vomiting
- Local anesthetic toxicity as evidenced by seizures or cardiovascular collapse without other reasonable etiology

Patients will be asked in the daily phone call if they or their family contacted anyone (any health care professional) regarding their pain overnight and that will be documented.

All data will be recorded on the Clinical Diagnostic Sheet and will then be given to the research coordinator for manual data entry. Data collection will continue until POD #14. At that time study participation will be terminated. Should patients be re-admitted to the

PROTOCOL TITLE: Prospective Randomized controlled study comparing liposomal bupivacaine to bupivacaine interscalene blocks for arthroscopic rotator cuff repair surgery

VERSION DATE: 8/5/2020

hospital in the next two weeks (Up to POD #30) for pain, a notation will be made in study records.

An analysis of the total cost of analgesics will be tabulated at the conclusion of the study to determine the most cost effective treatment option as this will be added into the cost of hospitalization including the number of days each patient spent in the hospital.

Blinding Procedure: The research assistant in this study will be blinded to the method of analgesia for the patient. The research assistant will assess pain one time per day. This person will not be responsible for any clinical testing and will record all data in the protected database daily. They will not have any access to the patients' clinical records or chart. **Any questions from the patient will be referred to the on-call resident or staff on call.**

5.2

Describe:

- The interscalene block is standard of care for patients and would be performed regardless of patient's participation in the study. All patients still would get preoperative multimodal treatment as well as an opioid sparing anesthetic.
- Patients would be required to take a dose of acetaminophen 975 mg oral and gabapentin 300 mg oral prior to surgery. They would then be required to receive an interscalene block with either liposome bupivacaine and bupivacaine or bupivacaine. Intraoperatively they would be required to receive propofol, lidocaine, ondansetron, dexamethasone, and ketamine for induction of anesthesia.

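### Section 5.1 instructs every patient to take scheduled ibuprofen at home (2,400 mg a day) with no exception, and section 8.2 leaves in patients with NSAID allergy, renal disease or peptic ulcer; an omit-and-record clause would close the gap

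*Combined protocol and SAP*

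**What the plan says.** The discharge paragraph of section 5.1 reads: "All patients will be discharged with instructions to take acetaminophen 975 mg q8 hours & ibuprofen 600 mg q6 hours". No exception, substitute or duration follows. The next sentence treats the opioid differently: "Additionally they will have opioid pain medication to take as needed for pain greater than 4". Ibuprofen is thus scheduled, while the opioid depends on pain.

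The same section writes other drugs for everyone. Before surgery, "All patients will receive preoperative oral multimodal medications consisting of acetaminophen 975 mg and gabapentin 300 mg", and at induction, "All patients will undergo a standard induction with propofol 1.5-3.0 mg/kg, ondansetron 4 mg, dexamethasone 10 mg and ketamine 0.25 mg/kg". Section 5.2 makes these compulsory; for the oral drugs it says "Patients would be required to take a dose of acetaminophen 975 mg oral and gabapentin 300 mg oral prior to surgery". Ibuprofen is not on the 5.2 list.

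The only written allergy substitute in the drug regimen concerns oral oxycodone in the recovery room: "or 2 mg of oral hydromorphone if allergic to oxycodone".

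Section 8.1 admits all adults having the operation. Section 8.2 lists seven exclusions, and the only drug allergy among them is to local anaesthetics. Section 5.1 (Assessments) also provides that "The amount of opioids used by the patient will be recorded as will any other adjuvant pain medication used".

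**The concern.** A universal instruction is safe only if eligibility removes the patients it would harm, or if the instruction carries its own exception. For ibuprofen the plan does the first only in part and the second not at all. A patient known to be allergic to NSAIDs meets 8.1, meets none of the exclusions in 8.2, and falls under the discharge instruction.

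Ibuprofen differs from the other fixed drugs because patients take it themselves at home, repeatedly and with no clinician present. What is at stake is avoidable harm to an eligible patient. A secondary matter is that a clinician who sensibly leaves the drug out departs from the protocol as written.

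**Working it through.** The plan states no figure on this point, so the check sets the sections side by side, with one dose calculation.

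**Dose.** Inputs from the 5.1 discharge sentence: 600 mg every 6 hours. Doses per day = 24 / 6 = 4. Daily dose = 4 x 600 = 2,400 mg. This describes the exposure instructed; it does not say how often harm would follow.

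**Eligibility.** Each 8.2 exclusion, and whether it removes a patient unsuitable for ibuprofen:

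| Exclusion in 8.2 | Removes such a patient? |
|---|---|
| Allergy to local anaesthetics | No |
| Daily opioid use for more than 3 weeks | No |
| Refusal | No |
| Coagulopathy | Yes, some |
| Non-English speaking | No |
| Pregnancy | Yes |
| No telephone | No |

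Two of seven help. None reaches NSAID allergy, renal disease or peptic ulcer. The documents do not say which conditions rule out ibuprofen. Renal disease and ulcer rest on general clinical knowledge, but NSAID allergy alone is enough to show the gap.

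**Other places where an exception could stand.**

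- 4.3 says what two of the drugs are for ("Acetaminophen is a medication used to treat pain, gabapentin is a gabapentinoid which is used to treat postoperative pain") but not who should avoid them, and does not mention ibuprofen.
- 5.1 has the oxycodone substitute and nothing equivalent for ibuprofen.
- 12.1 lets the surgeon withdraw a patient before surgery for a medical reason. This is optional and tied to no drug.
- 13.1 describes risks of surgery, the block and bupivacaine. Its standard-of-care statement rests on the two block options. Ibuprofen is not mentioned.

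Ibuprofen is named once in the documents, in the discharge sentence itself, so nothing elsewhere qualifies that sentence.

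**Effect of an omission on the trial.** Non-opioid use is collected under 5.1, 5.2 and 6.2, so an omission would be visible. A contraindication found at screening exists before allocation, which 5.1 places immediately before the block, so omission on that ground cannot depend on the arm. A patient who omits ibuprofen can stay in the trial.

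**The case against.** The strongest reply is that the risk is small in practice. Patients are seen in the surgeon's office or pre-assessment centre (8.3), treating clinicians would probably not send an NSAID-allergic patient home on ibuprofen, and the surgeon can withdraw a patient beforehand (12.1). The team calls at 24, 48 and 72 hours about complications and non-opioid drugs. Patients' questions go to staff on call, and safety data are reviewed weekly and monthly (17.2). The protocol sentence is also addressed to staff; the discharge paperwork a patient reads is not in these documents.

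Most of this stands, and it limits the point to a correction of wording. It does not remove the point. None of these safeguards names ibuprofen or requires its omission. At the nominal 24 hours of the first call about four doses may already have been taken. The blinded research assistant has no access to the chart (5.1, Blinding Procedure) and so could not check the history.

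A reader might infer three stronger claims that the documents do not support.

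- *That seven universally given drugs are all unguarded.* Acetaminophen, gabapentin, propofol, ondansetron, dexamethasone and ketamine are given around surgery with clinicians present, and 5.2 presents multimodal treatment and the opioid-sparing anaesthetic as care patients would receive anyway. The harm argued here is for ibuprofen only.
- *That 8.2 offers no protection at all.* Coagulopathy and pregnancy give some.
- *That the comparison of opioid use is biased or loses power.* Nothing in the plan shows this: the instruction is the same in both arms and departures from it are recorded.

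**Conclusion.** The point holds as a cheap improvement for patient safety. The plan instructs 2,400 mg of ibuprofen a day for all patients, with no exception. It excludes some patients for whom that is unsuitable, but not those with NSAID allergy, renal disease or peptic ulcer. This is more than missing detail, because a stated universal rule is unsafe for some eligible patients if it is followed.

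The conclusion assumes that the protocol is applied as written; clinical judgement would often intervene. The documents give no prevalence of contraindications, so the number of patients affected is unknown.

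**What to change.** In the 5.1 discharge sentence, add after the two drugs and doses: *unless allergic or contraindicated; omit the contraindicated drug, record the omission, and keep the patient in the trial*. Apply the same wording to the drugs that 5.2 calls required. Check for contraindications at the existing 8.3 screening or, for patients first approached on the day (11.1), in the preoperative area.

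The cost is two short text changes and one item at an existing contact, with no new data field. The downside is slightly less uniform background analgesia, visible in the non-opioid record.

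A new exclusion in 8.2 is not needed. It would narrow an all-adult, consecutively enrolled population for the same safety gain. For illustration, if 5% to 15% were newly excluded (an assumption; the documents give no figure), keeping 90 eligible patients would mean screening 90 / 0.95 = 94.7, so 95, to 90 / 0.85 = 105.9, so 106. Against the roughly 300 repairs a year in section 23.0, that is 32% to 35%, compared with 90 / 300 = 30%. The omit-and-record rule excludes nobody.

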1.0 Table of Contents

1.0	7
2.0	7
3.0	7
4.0	7
5.0	8
6.0	12
7.0	12
8.0	12
9.0	12
10.0	13
11.0	13
12.0	14
13.0	14
14.0	16
15.0	16
16.0	17
17.0	17
18.0	18
19.0	18
20.0	18
21.0	19
22.0	19
23.0	20
24.0	20

PROTOCOL TITLE: Prospective Randomized controlled study comparing liposomal bupivacaine to bupivacaine interscalene blocks for arthroscopic rotator cuff repair surgery

VERSION DATE: 8/5/11/2020

ABBREVIATIONS/DEFINITIONS

- LB/ liposomal bupivacaine
- RCR/rotator cuff repair
- QOR/Quality of Recovery
-

PROTOCOL TITLE: Prospective Randomized controlled study comparing liposomal bupivacaine to bupivacaine interscalene blocks for arthroscopic rotator cuff repair surgery

VERSION DATE: 8/5/2020

STUDY SUMMARY

Study Title	Prospective Randomized controlled study comparing liposomal bupivacaine to bupivacaine interscalene blocks for arthroscopic rotator cuff repair surgery
Study Design	Prospective randomized double blind study
Primary Objective	Total opioids in 72 hours
Secondary Objective(s)	Pain scores within 72 hours, QOR at 72 hours, Number of phone calls to surgeon, adverse events, time to discharge
Research Intervention(s)/Investigational Agents	Liposomal bupivacaine and bupivacaine vs bupivacaine
Scientific Assessment	HRPP facilitated scientific assessment
IND/IDE # (if applicable)	Study Medication has been approved for use in shoulder surgery April 6, 2018
IND/IDE Holder	n/a
Investigational Drug Services # (if applicable)	n/a
Study Population	Adult patients aged 18 and older who are undergoing arthroscopic rotator cuff repair surgery
Local Sample Size (number of participants recruited locally)	90

PROTOCOL TITLE: Prospective Randomized controlled study comparing liposomal bupivacaine to bupivacaine interscalene blocks for arthroscopic rotator cuff repair surgery

VERSION DATE: 8/5/2020

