6.0 Data and Specimen Banking

- 6.1 *Storage and Access:* All study data will be stored on excel spreadsheets stored in Box. Only the PI and members of the research team will have access to the data.
- 6.2 *Data:* The data from this study will be collected both from Epic and directly from the patient. The data collected includes: demographic data, age, weight, ASA class, duration of surgery, length of stay in recovery room both phase 1 and 2, amount of opioids given intraoperatively and post-operatively, non-opioid pain medication, pain score (0-10) at 2, 6, 24, 48, and 72 hours, satisfaction with treatment, Quality of Recovery survey at 72 hours and 14 days, and any adverse events.
- 6.3 *Release/Sharing:* N/A

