13.0 Risks to Participants

13.1 Foreseeable Risks: The study has the following risks:

- infection
- bleeding
- nerve injury
- cardiac arrhythmias (irregular heartbeat)
- respiratory complications

PROTOCOL TITLE: Prospective Randomized controlled study comparing liposomal bupivacaine to bupivacaine interscalene blocks for arthroscopic rotator cuff repair surgery

VERSION DATE: 8/5/2020

These complications all fall within the standard risks of surgery and the performance of the interscalene injection. Any intervention being provided as a part of this study falls within the standard of care as both medication options are within the standard treatments for post-operative pain and are currently used as analgesic options at UMMC.

EXPAREL contains bupivacaine. Serious side effects related to bupivacaine are not common, but may occur if too much is given or if it is accidentally injected into a blood vessel. When given incorrectly, side effects may involve the brain or the heart.

The effects on the brain and central nervous system may include:

- Restlessness (< 2%)
- Anxiety (<2%)
- Dizziness (<2%)
- Tinnitus (ringing in the ears) (<2%)
- Blurred vision (<2%)
- Tremors (shaking) possibly proceeding to convulsions (<2%).

The effects on the heart appear when too much bupivacaine is given or when bupivacaine is injected in a blood vessel by accident. These effects cause a decrease of the heart function, including low heart rate or abnormal heart rhythm, decreased blood flow, low blood pressure, and, in extreme cases, heart attack. (<2%)

The numbing sensation caused by bupivacaine may be persistent, with slow, incomplete, or no recovery. Sometimes a tingling sensation may appear in the area treated with bupivacaine. When injected next to a large nerve, bupivacaine may cause weakness or paralysis.

Allergic reactions are rare, but may include rash, itching and redness of the skin, sneezing, nausea, vomiting, dizziness, fainting, sweating, fever, and low blood pressure.

Other side effects of liposomal bupivacaine when given into the wound include:

PROTOCOL TITLE: Prospective Randomized controlled study comparing liposomal bupivacaine to bupivacaine interscalene blocks for arthroscopic rotator cuff repair surgery

VERSION DATE: 8/5/2020

- Nausea (22.6%)
- Constipation (8.7%)
- Vomiting (6%)
- High temperature (5.5%)
- Dizziness (<2%)
- Swelling (<1%)
- Low blood pressure (<2%)
- Anemia (<1%)
- Itching (2.4%)
- High heart rate (1.3%)
- Headache (5%)

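### The only named nausea and vomiting item is tied to opioid cause with no attribution rule, so a comparison of arms on it depends on the primary outcome; the named toxicity item covers only the severe end of the listed signs.

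*Combined protocol and SAP*

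**What the plan says.** The Study Summary puts adverse events among the secondary objectives: "Number of phone calls to surgeon, adverse events, time to discharge". The complications list in section 5.1 (Assessments) has two items that matter here:

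- "Opioid related side effects of nausea and/or vomiting"
- "Local anesthetic toxicity as evidenced by seizures or cardiovascular collapse without other reasonable etiology"

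The list opens with "All complications will be recorded including", so it gives examples and is not closed. Section 5.2 has adverse events among the data gathered at patient interviews, and section 6.2 closes its data list with "Quality of Recovery survey at 72 hours and 14 days, and any adverse events".

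Section 13.1 gives the risks. Under "Other side effects of liposomal bupivacaine when given into the wound include" it lists nausea at 22.6% and vomiting at 6%. For bupivacaine it lists restlessness, anxiety, dizziness, tinnitus, blurred vision and tremor, each below 2%. It also lists cardiac effects that include "low heart rate or abnormal heart rhythm, decreased blood flow, low blood pressure, and, in extreme cases, heart attack", again below 2%.

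No section defines or grades adverse events, or says how an episode of nausea is judged to be opioid related. Section 15.3 leaves the analysis to a statistician who is to work from the protocol.

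**The concern.** The nausea item builds a presumed cause into the outcome. Whether an episode can be called opioid related depends on whether, and how much, opioid the patient took. Opioid use over 72 hours is the primary outcome, and the trial expects LB to lower it. The item is therefore conditioned on something that treatment is meant to change after randomisation. An all-cause count does not have this problem.

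At stake is the reading of a secondary safety objective. Fewer opioid-related episodes with LB could be reported as better tolerability, when part of the difference comes only from the label. The primary analysis is not affected.

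The toxicity item is a smaller matter. It names the extreme presentations and leaves the milder signs in section 13.1 without a category, so they may be recorded but not summarised consistently by arm.

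**Working it through.** The plan states no figure on this point that could be reproduced, so the check is mainly a comparison of texts, with some arithmetic to show what can and cannot be sized.

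**Texts side by side**

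- Nausea and vomiting: section 5.1 names them under an opioid cause, and section 13.1 names them under LB. One symptom has two possible causes in the protocol and no rule for choosing between them.
- Toxicity: section 5.1 names seizure and cardiovascular collapse. Section 13.1 names six milder neurological signs, and cardiac signs short of collapse.
- General capture: sections 5.1, 5.2 and 6.2 allow any other event to be recorded, but give it no defined category.

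**Mechanism**

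Let N be the proportion of an arm with any nausea, and q the share of those patients judged opioid related. The named item estimates N × q in each arm. If N is the same in both arms, the difference (control minus LB) is

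N × (q_control − q_LB).

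This is zero when q is equal. It is positive, and so favours LB, when lower opioid use makes q smaller in the LB arm. The all-cause count estimates N directly and does not involve q.

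**What can be sized**

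Assumptions: the 70 patients of section 15.2 split equally, so 35 per arm (no allocation ratio is stated), and the wound-use rates of section 13.1 carried over to the block.

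- Nausea: 35 × 0.226 = 7.9 patients in an arm.
- Vomiting: 35 × 0.06 = 2.1 patients in an arm.

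These are total counts under a borrowed rate. They show that nausea may be common enough for its label to matter, but they do not measure how many patients are misclassified. That needs q in each arm, and the documents give neither q nor the number of patients expected to take no opioid. If N were 22.6% in both arms and q no higher with LB, the formal limits for the distortion run from 0 patients (equal q) to 7.9 (q of 1 against 0). That range is too wide to count as an estimate.

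**Toxicity signs**

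For one sign at the 2% ceiling:

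- Expected cases per arm: 35 × 0.02 = 0.7.
- Chance of at least one case in 35: 1 − 0.98^35 = 51%.
- Chance of none in 70: 0.98^70 = 24%.

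Section 13.1 gives no separate rate for seizure or collapse.

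**The case against.** The strongest reply is that nothing is lost. The complications list is open-ended, any adverse event is collected, and the secondary objective is adverse events, not the items on that list. This stands as far as recording goes. A reader might infer that nausea is counted only when opioid related, or that milder toxicity signs are excluded; the documents do not support either. But recording an event does not classify it, and for nausea and vomiting the protocol offers no other category on which to compare arms.

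A reader might also take the general capture to be unsolicited. That is not supported. Section 5.2 places adverse events within patient interviews, section 5.1 has calls that ask about signs of complications, and the recording forms are not in the documents.

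A further reply is that an LB patient whose nausea is credited to an opioid still counts under the item, and that episodes judged not opioid related drop out in both arms. Both statements are correct. The rule is the same in each arm, but its effect is not if opioid use differs, and that difference is what the trial is designed to show. Blinding the research assistant limits judgement by known arm. It does not remove the dependence on opioid use, since the 24, 48 and 72 hour calls ask for pills taken.

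Finally, a risk disclosure is not a case definition, and a specific toxicity definition is defensible. Restlessness, anxiety and dizziness are non-specific in patients who may receive midazolam, propofol, gabapentin and ketamine. This stands, and is why the milder signs should not be counted automatically as toxicity.

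**Conclusion.** The point holds as a matter of definition. The named nausea and vomiting item is conditioned on opioid cause, has no attribution rule, and could favour LB if it is used to compare arms. The direction rests on LB lowering opioid use and on attribution following opioid intake. The size cannot be estimated from the documents. The toxicity gap is secondary.

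Two stronger readings are not supported. First, the 7.9 and 2.1 patients are not events caused by LB: the rates are for wound use, have no comparator, and are carried over to a trial in which all patients are to receive ondansetron and dexamethasone. Second, it does not follow that the trial is almost bound to report no toxicity. At the 2% ceiling, no events in 70 patients has a 24% chance. A lower true rate would raise that chance, but the documents give none for the qualifying events.

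**What to change.** In section 5.1, replace the opioid-related item with nausea and vomiting, each recorded yes/no in every patient regardless of presumed cause, at the contacts already planned at 2, 6, 24, 48 and 72 hours. Compare arms on that all-cause count. If a judgement of cause is still wanted, report it separately as description, with the rule stated.

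Keep seizure or cardiovascular collapse as the severe toxicity category. Alongside it, record the neurological and cardiac signs already named in section 13.1, with time from injection, and report them by arm as signs and not automatically as toxicity cases.

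The cost is a change of wording, a short checklist at contacts already scheduled, and more minor events reported in both arms.
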